4.17.11.5 Data Listing

Individual subject data will be listed with their positive/negative status, titer information (spot forming units (SFU) for ELISpot assay) and AEs of interests (as mentioned above) where available. The impact of assay status (positive/negative, treatment-emergent positive yes/no) on clinical efficacy may be further evaluated if needed.

4.17.12 Vector Shedding

Samples of vector shedding will be summarized by categorical results and will be tabulated by visit, by period and eyes. Categorical results include but not limit to Positive, Negative and Below the Level of Quantification. The data of vector shedding will be listed.

4.17.13 Vital Signs

Blood pressure and pulse rate and change from baseline will be summarised by visit and by period.

4.18 Protocol Violations or Deviations

Deviations from the protocol will be documented on an ongoing basis by the study monitors/project manager throughout the study period.

4.19 Deviations from the Statistical Analysis Plan

Any deviations from the original statistical plan will be described and justified in the final clinical study report.

4.20 Changes in Planned Analyses from the Protocol

There are some changes to the planned analyses described in the protocol.

1. The protocol refers to the assessment of Fixation Location. Because of a change in the way microperimetry data are collected, fixation location is not available in the database. Therefore, Fixation Location was removed from the SAP.
2. The protocol mentions that specific analyses of the sensitivity points (microperimetry) will be performed. These analyses are not included in the SAP as they are considered as exploratory across the BIIB111 program and will be performed as post-hoc analyses, if needed to be consistent with other studies in the same program.
3. For consistency of other studies in the program, time to resolution of AEs will not be summarized.
3. The protocol specifies that LOCF will be used as imputation method for efficacy analyses. The main analyses of categorical and continuous efficacy endpoints will use the observed case method, as the main purpose of the study is the evaluation of BCVA from a safety perspective. Additional supportive analyses of BCVA-related endpoints, including LOCF imputation, will be applied and are described in detail in [Section 4.16.1](#).

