1997, Cheng, Azen et al. 2001, Anderson, Fineman et al. 2006, Stein, Zacks et al. 2009, Recchia, Scott et al. 2010). Post-operative intraocular inflammation caused by vitrectomy is often associated with transient or sometimes permanent visual impairment. Another complication of vitrectomy is cataract formation, which may require an additional surgical procedure (cataract extraction) (Park, Marcus et al. 1995, Cheng, Azen et al. 2001, Recchia, Scott et al. 2010). In addition, the surgical procedure is performed under general anesthesia, which includes the risks of dizziness, confusion, nausea and vomiting.

Loss of VA has been observed post-treatment with AAV2-REP1. This VA loss was determined by the Investigators to be plausibly related to the administration of AAV2-REP1, however without definitively attributing the cause to either the study procedure or the GTMP. Complications from the surgical procedure are expected and are not considered reportable as suspected unexpected serious adverse reactions (SUSARs) unless also assessed to be at least possibly related to AAV2-REP1. The Reference Safety Information described in the current version of the Investigator's Brochure for AAV2-REP1 defines *visual acuity reduced* as an expected serious adverse drug reaction, with a frequency of 4/79 (5.1%), defined as common ($\geq 1/100$ to $<1/10$). Loss of VA is considered an identified risk of AAV2-REP1. Inflammation is a potential risk of AAV2-REP1.

See the Investigator's Brochure for further details.

Thus, although there are risks associated with the administration of the study treatment via vitrectomy and retinal detachment, the potential for benefit in the form of improved VA that may be provided to subjects with CHM following treatment with AAV2-REP1 provides an acceptable risk-benefit profile for participation in this study.

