The interval between SE1 and SE2 treatment is expected to vary among subjects from weeks to many months. While the interval will be decided on a case-by-case basis, an effort will be made to schedule varying treatment intervals in order to better characterise the immunological and safety profile of sequential treatment administration. Thus, approximately 20 subjects each will be treated with a short- (<6 month), medium- (6-12 months), or long- (>12 month) surgery window between treatment of the first and second

eye. Because the timing of the second surgery visit (Period 2, Visit 1) will vary among subjects, the duration of study Period 1 will also be variable.

The post-operative outcome and visual function of SE1 will inform the scheduling of Period 2. Signs of post-operative inflammation or other post-operative sequelae, as judged by the Investigator, should be resolved in SE1 for the subject to continue to Period 2. After comprehensive evaluation of all safety assessments and visual functional tests of SE1 and SE2, the Investigator will determine the eligibility of the subject and decide the appropriate time to schedule SE2, Visit 1.

All baseline ophthalmic assessments must be conducted within 10 weeks prior to SE2 surgery (Period 2, Visit 1). If these assessments are not available within the required timeframe, a Baseline Visit must be added to collect current baseline data on SE2. Study eye selection and eligibility for surgery will then be confirmed collectively by the Patient Eligibility Review Committee, which includes the Investigator, a consulting surgeon, and the Sponsor (see the Patient Eligibility Review Plan). If, at that time, BCVA in SE2 is <34 ETDRS letters, surgery may be performed when, in the opinion of the Patient Eligibility Review Committee: 1) the subject is found eligible by all other inclusion and exclusion criteria, and 2) the subject is considered an appropriate candidate who has potentially modifiable disease.

At Period 2, Visit 1 (Day 0, Injection Day Visit for SE2) subjects will undergo a vitrectomy with retinal detachment and sub-retinal injection of AAV2-REP1 in the contralateral, untreated eye (SE2). Post-treatment, subjects will no longer follow the Period 1 visit schedule, but will instead attend Period 2, Visits 2-9 according to the Schedule of Study Procedures. Ophthalmic assessments scheduled for Period 2, Visits 2-9 will be performed on both eyes.

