13.6.7 Adverse Events

AEs will be coded using the Medical Dictionary for Regulatory Affairs, version 21.0 or higher. Events will be summarised by system organ class and preferred term and eye. The number of eyes with an AE, as well as the number of events, will be summarised, by period and eye. Similar summaries will be produced for study drug/procedure-related AEs, AEs leading to discontinuation, and SAEs. AEs will also be summarised by maximum severity, relationship to study drug/procedure, and time to onset and resolution.

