4.3 Definitions

Study Eye 1 (SE1) is defined as the first treated eye (within GEMINI or in an antecedent clinical trial). **Study Eye 2 (SE2)** is defined as the second treated eye (irrespective of whether the first eye was treated in GEMINI or in an antecedent clinical trial). Subjects whose first eye is treated in an antecedent study will contribute to Period 2 only (except for the immunogenicity analyses), where Study Eye 1 is the eye treated in the antecedent study and Study Eye 2 is the eye treated in GEMINI.

Period 1 starts on the day of the surgery of the first treated eye and ends on the day prior to the day of the surgery of the second treated eye. **Period 2** starts on the day of the surgery of the second treated eye.

Baseline Value of Period 1/2 is defined as the last non-missing value prior to treatment of the respective period. Baseline of each period for each eye will be used to calculate the change from baseline for the data in the same period and same eye. For example, period 1 SE1 baseline will be used to calculate the change from baseline for all the data of SE1 in period 1, whereas period 2 SE1 baseline will be used to calculate the change from baseline for all the data of SE1 in period 2.

For immunogenicity, baseline will be defined separately in [Section 4.17.11](#).

Analysis day for all the post-baseline visits will be calculated as the date of the post-baseline visits minus the corresponding injection date, depending on which baseline that was used.

For the 6 subjects whose first eye was treated in the antecedent study (Subjects [REDACTED], [REDACTED], [REDACTED]), only period 2 data are collected in GEMINI. Therefore, only period 2 data will be presented for these 6 patients.

Change from Baseline is defined as the difference of the value of an assessment at the considered visit from the baseline value of the corresponding period.

Duration is measured in days and is calculated as end date – onset date + 1.

Injection dates of SE1 and SE2 will be coded **Day 0** for the Period 1 and Period 2 respectively.

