Both counts of subjects and events will be reported. A subject with more than one occurrence of the same AE in a particular SOC will be counted only once in the total of those experiencing AEs in that particular SOC.

If a subject experiences the same AE at more than one severity, the most severe rating will be given precedence.

If a subject experiences the same AE at more than one relationship to study drug/procedure, causal relationship will be given precedence over no causal relationship. However, where a causal relationship is identified by the Investigator, the subject will be counted once within each sub-category (Study Drug, Study Procedure, Study Drug and Study Procedure, unknown).

In the summary tables, related events are defined as events that are assessed by the investigator to be related to study drug/procedure/both or with an unknown relationship.

AEs will be assigned to Period 1 or Period 2 based on the AE Start Date. An AE with a start date on or after the day of surgery of Study Eye 2 will be attributed to Period 2; otherwise, the AE will be attributed to Period 1.

An ocular event is an event where the site of the event is reported as OU, OD or OS. Where an event is recorded as 'OU', it will be counted once for each eye (SE1 and SE2).

Separate additional summaries will be provided for adverse events classified as Ocular Inflammation and Visual Acuity Reduced. The lists of PTs assigned to Ocular Inflammation and Visual Acuity Reduced are provided in a separate document (BIIB111 Signal Detection Plan). The following summaries will be provided by eye, by period (or by surgery window), and overall:

- Ocular Inflammation-related TEAEs by SOC and PT
- Ocular Inflammation-related TEAEs by SOC and PT, and by time to onset (≤ 30 days; > 30 days)
- Visual Acuity Reduced-related TEAEs by SOC and PT
- Visual Acuity Reduced-related TEAEs by SOC and PT, and by time to onset (≤ 30 days; > 30 days)

Imputation rules for partial dates are presented in Appendix 7.1.

The following listings will be provided:

- All AEs
- AEs leading to death

AEs will be coded according the MedDRA version 23.0 or higher.

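### The SAP drops the protocol's time-to-resolution summary for programme consistency alone, so its Ocular Inflammation and Visual Acuity Reduced tables show onset but not resolution or duration

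*SAP*

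**What the plan says.** - **Protocol 13.6.7**, repeated in the synopsis: "AEs will also be summarised by maximum severity, relationship to study drug/procedure, and time to onset and resolution".
- **SAP 4.20**: "time to resolution of AEs will not be summarized", the stated reason being consistency with other studies in the programme. No reason specific to this trial follows. Of the other changes listed there, Fixation Location goes because the data are not in the database, and LOCF becomes supportive because of this study's safety purpose. The sensitivity-point analysis, like time to resolution, is set aside on programme grounds.
- **Protocol 5.4**: "Loss of VA is considered an identified risk of AAV2-REP1. Inflammation is a potential risk of AAV2-REP1".
- **SAP 4.17.10**: "Separate additional summaries will be provided for adverse events classified as Ocular Inflammation and Visual Acuity Reduced". Each group gets one table by system organ class and preferred term and one that adds an onset split, for example "Visual Acuity Reduced-related TEAEs by SOC and PT, and by time to onset", cut at 30 days. All are by eye, by period or surgery window, and overall. None is split by outcome or duration.
- **SAP 4.3**: "Duration is measured in days and is calculated as" end date minus onset date plus one. No adverse event summary in SAP 4.17.10 uses it.
- **Protocol 11.1.2**: onset date, end date and outcome are recorded for each event, and ocular events are recorded per eye.

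**The concern.** For these two event types, how long the event lasts is much of the clinical meaning. Protocol 5.4 notes that inflammation after vitrectomy can bring visual impairment that passes or that stays. Protocol 7.1 treats resolution as material, since post-operative signs "should be resolved in SE1 for the subject to continue to Period 2". Yet in the tables devoted to these events, an inflammation that clears in two weeks and one still present at Month 12 each count as one event with the same onset class.

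The trial gives the same product to the second eye after the first. Whether inflammation or acuity loss resolves as often and as quickly after the second treatment is a natural safety question here. The reason given for dropping the summary refers to other studies and does not address that question.

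**Working it through.** The plan states no figure to reproduce. The check sets the planned outputs side by side, then looks at what they can and cannot show.

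**1. Planned outputs that bear on persistence**

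| Output | What it shows | What it leaves out |
|---|---|---|
| Two event-group tables (SAP 4.17.10) | Onset up to or after 30 days | Outcome, end date, duration |
| TEAE by outcome (SAP 4.17.10) | Subjects by outcome, by period or surgery window | Not restricted to the two groups; no duration |
| Serious TEAEs (SAP 4.17.10, definition in Protocol 11.1.1.2) | Surgery-related loss of 15 or more letters becomes serious if not recovered by Month 1 | Non-surgical loss need only exceed 48 hours; inflammation has no comparable duration rule |
| Letter losses of at least 5, 10 and 15 (SAP 4.17.1) | Eyes affected at each visit | Does not follow the same eye between visits |
| Supportive SE1 remapping (SAP 4.16.1) | SE1 acuity against its Period 1 baseline, windows to Month 24 | BCVA and SE1 only; group level |
| Immunogenicity and safety (SAP 4.17.11.4) | Loss of 15 or more letters at Month 12; both event groups by severity and onset | Resolution |
| Slit lamp (SAP 4.17.3) | Hypopyon, cells, flare and vitreous inflammation by visit, with shifts | Shifts run from baseline to visit, not from onset to end of an event |
| Listing of all AEs | Each event | No summary |

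**2. Why by-visit counts do not give resolution.** Suppose *a* of *n* eyes are affected at Month 1 and *b* at Month 12. The number affected at both lies between max(0, *a* + *b* − *n*) and min(*a*, *b*). With assumed counts (not from the documents) and *n* = 60:

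- *a* = 6, *b* = 6: max(0, 12 − 60) = 0 to min(6, 6) = 6
- *a* = 12, *b* = 6: max(0, 18 − 60) = 0 to 6
- *a* = 3, *b* = 3: max(0, 6 − 60) = 0 to 3

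Six affected eyes at each visit could thus be the same six eyes throughout, or six early losses that all resolved and six new ones.

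**3. Baseline reset in SE1.** SAP 4.3 gives SE1 a new baseline at Period 2. A 15-letter loss that is still present at that baseline and stays unchanged counts as −15 in Period 1 and 0 in Period 2. Only the supportive remapping keeps it at −15, and that is specified for BCVA alone.

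**4. Likely number of events (illustration).** Inputs: about 60 subjects (Protocol 13.1), 6 of them with the first eye treated in an antecedent study (SAP 4.3 and 4.4), and 4/79 for serious visual acuity reduced (Protocol 5.4).

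- Eyes treated in this study: (60 − 6) × 2 + 6 = 114
- Expected eyes: 114 × 4/79 = 5.8
- Exact 95% interval for 4/79 is 1.4% to 12.5%, so 114 × 0.014 = 1.6 to 114 × 0.125 = 14.2 eyes
- By eye: SE1 54 × 4/79 = 2.7; SE2 60 × 4/79 = 3.0

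**The case against.** The case for leaving the SAP alone is a fair one.

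- A reader might infer that no planned table separates transient from persistent inflammation or acuity loss, or that the trial could not compare the first and second exposures. The documents do not support either reading. The letter-loss tables distinguish a Day 1 loss that has gone by Month 1 from loss present at Month 12. The slit-lamp tables allow SE1 in Period 1 and SE2 in Period 2 to be compared visit by visit on examined signs.
- SAP 4.17.10 says generally that ocular TEAEs are summarised by eye, so the outcome count may also be available by eye. Only the restriction to the two event groups is missing.
- The serious-event definition already removes most surgical losses that recover, so the 4/79 rate is a poor guide to transient events.
- The SE1 resolution condition is an investigator's judgement on each subject during the study; no final table feeds it. Protocol 13.1 names the immunological profile as the key concern, and neither document calls duration of inflammation the central question.
- The change is declared in the proper section of a descriptive study, and all events are listed.
- With about three serious acuity events per eye, a Kaplan-Meier median would say little. Duration in SAP 4.3 is undefined for unresolved events, and SAP Appendix 7.1 can move partial end dates to the end of the month or year, which lengthens durations.

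All of this stands as a limit on the point. It does not close the gap: the group-level tables do not link an event or an eye to its resolution, the outcome count is not confined to the two groups, and a listing leaves the reader to compile the summary the protocol promised.

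**Conclusion.** The point holds in a limited form. A summary specified in the protocol was removed without a reason tied to this trial. For the two event groups the SAP itself singles out, the tables report onset but neither resolution nor duration. Persistence can be inferred at group level from other outputs; what is missing is how many of these events resolved, and how long they lasted, after the first and after the second treatment.

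This affects the completeness of the safety report, not the validity of the trial. The figure of about 6 of 114 eyes covers serious visual acuity reduced only. It assumes 60 subjects, every second eye treated (Protocol 8.3 allows otherwise) and a per-eye rate, although the protocol does not say whether the 79 are eyes or subjects. The documents give no rate for inflammation or for non-serious acuity events.

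**What to change.** In SAP 4.17.10, for the Ocular Inflammation and Visual Acuity Reduced TEAEs only, by eye and by period of onset, add:

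- the number and percentage of events resolved and unresolved at last contact;
- for resolved events, duration by the SAP 4.3 definition, summarised descriptively;
- for unresolved events, time from onset to last contact, marked as censored. SE1 events can be followed through Period 2 and so for longer than SE2 events, so these times belong beside the counts;
- a Kaplan-Meier estimate only if the counts allow it;
- a flag on durations that rest on imputed end dates.

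Amend SAP 4.20 to say that time to resolution stays dropped for all other adverse events.

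The cost is one or two extra tables from onset date, end date and outcome, all already collected. The drawback is small counts and wide intervals, so the tables will describe rather than compare.

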4.21 Algorithms/SAS Codes

- **Descriptive statistics for continuous variables:**

```
PROC UNIVARIATE DATA=dset NOPRINT;
  VAR var1 var2 var3 ...varn;
  BY byvar; (optional)
  OUTPUT OUT=outname
  N=n MEAN=mean MIN=min MAX=max MEDIAN=median STD=std
  P5=p5 P95=p95 Q1=q1 Q3=q3;
RUN;
```

- **95% CIs for continuous variables – ttest formula:**

```
DATA outdata;
  SET outname;
  LCL=mean-(TINV(0.975,n-1)*(std/SQRT(n)));
  UCL=mean+(TINV(0.975,n-1)*(std/SQRT(n)));
RUN;
```

- **Frequency counts:**

```
PROC FREQ DATA=dset NOPRINT;
  BY byvar; (optional)
  TABLES var1*var2;
  OUTPUT OUT=outname;
RUN;
```

- **Clopper-Pearson 95% CIs within group for binomial proportions:**

```
DATA outdata;
  SET outname;
  p=round ((x/n),0.0001);
  if p=0 then LCL=0;
  if p=1 then UCL=1;
  if p ne 0 then LCL=round((1-betainv(.975,(n-x+1),x)),.0001);
  if p ne 1 then UCL=round((1-betainv(.025,(n-x),x+1)),.0001);
RUN;
```

5 Tables and Listings

5.1 Format

All outputs will be produced using SAS version 9.4 or a later version.

A header will include the following text: NightstaRx, Ltd NSR-REP-02 <FINAL ANALYSIS>

In the top left portion of each table/listing, a *table/listing number* followed by the *title* of the table/listing will be presented. After the title line, optional *sub-title* or *population* information can be presented. Horizontal lines will appear before and after the column heading of the table/listing. *Footnotes* will be put under the main body of text at the bottom of the page.

The *sponsor name*, *protocol number*, programmers User ID, status of the table/listing (i.e. draft or final) and *SAS program name* will appear bottom left in a string and the *page number* will appear on the bottom right corner of each table/listing. The *date and time of creation* of table/listing will appear bottom left under the sponsor name. The source listing number will appear bottom left.

A *landscape layout* is proposed for both table and listing presentations.

In a listing, in the case that a subject's record has been continued to the next page, an appropriate identification (e.g., the subject ID number) must be presented at the beginning of that page.

Outputs will be produced as rtf files. The output file name will include the table number and name.

5.2 Conventions for output display

Unless otherwise specified, in summary tables of continuous variables, the minimum and maximum values will be displayed to the same number of decimal places as the raw data, the mean and median will be presented to one extra decimal place compared to the raw data, and the SD will be displayed to two extra decimal places compared to the raw data. Wherever possible data will be decimal aligned.

Unless otherwise specified frequency tabulations will be presented by number and percentage, where the percentage is presented in brackets to 1 decimal place.

Any date information in the listing will use the date9. format, for example, 07MAY2002. In the listing, a unit associated with a variable will be presented only once within parentheses either below or next to that variable in the heading portion. If a parameter has multiple units, each unit will be displayed only once, as applicable.

All tables will have their source listing referenced in a footnote. **Listings should be sorted by subject number, eye (starting with Study Eye or Study Eye 1) and visit.** Listings should have the source data received from data management referenced in a footnote.

6 References

MAIA, Macular Integrity Assessment, Microperimetry Handbook, First Edition, Centervue.

7 Appendices

7.1 Appendix 1 – Imputation of Partial Dates

These imputation rules are limited to AE and CM partial dates only.

Partial start dates (of intervention or event)

- Case 1, day is missing (only month and year are present):
 - If year and month are same as treatment period start date then assign the day of treatment period start date to the partial date.
 - However, if end date of event or intervention is clearly before treatment period start date, assign day ‘01’ to partial start date.
 - Otherwise, assign day of ‘01’ to partial start date.
- Case 2, only year is present:
 - If year is same as treatment period start date then assign the month and day of the treatment period start date to the partial date.
 - However, if end date of event or intervention is clearly before treatment period start date, assign ‘Jan. 01’ to partial start date.
 - Otherwise, assign the month and day of ‘Jan. 01’ to partial start date.
- Case 3, completely missing date, no imputation is performed.

Partial end dates (of intervention or event)

- Case 1, day is missing (only month and year are present):
 - If year and month are same as study end date then assign the day of the study end date to the partial date.
 - Otherwise, assign day of last day of the month (28, 29, 30 or 31) to the partial end date.
- Case 2, only year is present:
 - If year is same as study end date then assign the month and day of the study end date to the partial date.
 - Otherwise, assign ‘Dec. 31’ to the partial end date.
- Case 3, completely missing date, no imputation is performed.

Note: If any partial dates have missing month, with day present, then day is ignored and also considered missing. Similarly, if year is missing, with day or month present, we handle as if the entire date is missing.

Note: If the study is ongoing and study end date is not available then the cut-off date will be used in the place of study end date. If both a cut-off date and study end date are present for a patient then the minimum of the two dates will be used as the study (or reference) end date.

